### **6.6.2. NA Re-treatment Criteria and Monitoring after Stopping of NA**

Participants who meet the NA treatment completion criteria outlined in Section [6.6.1](#) will be monitored closely during the follow-up phase.

After stopping NA treatment, participants should be monitored as follows:

- Regular monitoring visits will be every 4 weeks during the follow-up phase in accordance with the [Schedule of Activities](#).

- A post-treatment HBV DNA value of >20,000 IU/mL should trigger re-testing of ALT/AST, HBV DNA, and total and direct bilirubin within a maximum of 7 days from receipt of the data and further repeats as necessary (ie, weekly until HBV DNA returns to <20,000 IU/mL).
- A post-treatment HBV DNA value of >2,000 IU/mL (but <20,000 IU/mL) should trigger a re-test within 14 days from receipt of the data and further repeats as necessary (ie, every other week until HBV DNA returns to <2,000 IU/mL).
- A post-treatment ALT value of >5x ULN should trigger re-testing of ALT, AST, ALP, total and direct bilirubin, INR, albumin, and HBV DNA on a weekly basis until ALT and AST levels have returned to <5x ULN.

After stopping NA treatment, participants should re-start NA treatment:

- Immediately with signs of decreasing liver function based on laboratory findings (eg, INR, direct bilirubin) or clinical assessment (eg, ascites, hepatic encephalopathy),
- Immediately with an HBV DNA value of >100,000 IU/mL (irrespective of confirmation and/or ALT increase).
- With confirmed post-treatment HBeAg seroreversion (HBeAg positive after it was negative at NA completion)
- With confirmed\* post-treatment increases in HBV DNA >2,000 IU/mL and ALT >5x ULN
- With confirmed\* post-treatment increases in HBV DNA >20,000 IU/mL.

*\* At least 4 weeks apart frequency of visits as described above*

**Note:**

Additional re-testing and/or earlier restarting of NA treatment is at the investigator's discretion, even if the above cut-offs are not yet met.

To avoid delays in decision making, sites are encouraged to run local re-testing in parallel with central re-testing in the situations described above that require more frequent re-testing. Local test results are to be recorded in the CRF and/or source documents, including information on the HBV DNA assay used. In addition, to avoid delays in NA re-treatment, it should be considered to dispense NA to participants who potentially met the NA re-treatment criteria (eg, pending confirmation) and who will not be available to come to the study site immediately at the time the confirmatory test results will become available. This should ensure that the participant can immediately re-start NA treatment if indicated, upon direct confirmation by the investigator.

In case NA treatment is re-started, participants will be followed until the end of the study or until clinical stabilization, whichever comes later.

Refer to Appendix 12 in Section 10.12 for a graphical representation.

## 6.7. Study Intervention After the End of the Study

Participants will be instructed that study intervention will not be made available to them after they have completed/discontinued study intervention and that they should return to their primary physician to determine standard of care.

The investigator should consider to re-start NA treatment per local standard of care at the EOS visit (Follow-up Week 48 up to maximum Follow-up Week 72) for participants who met the NA treatment completion criteria at Week 48 or for participants who met NA treatment completion criteria at the end of treatment with PegIFN- $\alpha$ 2a during the follow-up phase, who did not re-start NA treatment during the follow-up phase, and who did not achieve and maintain HBsAg seroclearance. NA will not be provided by the sponsor after the final study visit.

## 7. DISCONTINUATION OF INVESTIGATIONAL INTERVENTION AND PARTICIPANT DISCONTINUATION/WITHDRAWAL

### 7.1. Discontinuation of Study Intervention

With the implementation of Protocol Amendment 5, all participants had to stop JNJ-6379 treatment immediately.

Treatment with JNJ-3989 and/or PegIFN- $\alpha$ 2a must be discontinued if any of the criteria listed below apply. If JNJ-3989 is discontinued, PegIFN- $\alpha$ 2a should also be discontinued. If PegIFN- $\alpha$ 2a is discontinued, JNJ-3989 should be continued. NA treatment may be continued or, in consultation with the sponsor or discontinued based on investigator judgement.

- The participant withdraws consent to receive study intervention.
- The investigator believes that for safety reasons or tolerability reasons (eg, AE) it is in the best interest of the participant to discontinue JNJ-3989 (and, if applicable, PegIFN- $\alpha$ 2a).
- The participant becomes pregnant.
- The participant has a  $\geq$ grade 3 rash (see Section 10.5, Appendix 5, Rash Management) or allergic reaction (see Section 8.5.7.2).
- The participant has signs of hepatic decompensation (ie, clinical evidence of ascites, bleeding varices, or hepatic encephalopathy) or an increase in direct bilirubin  $>1.5$ x ULN in combination with INR  $\geq 1.5$ x ULN or albumin  $<3.0$  g/dL.
- The participant has a confirmed  $\geq$ grade 3 eGFRcr abnormality and a drop from baseline of  $>10$  mL/min/1.73 m^2, considered at least possibly related to JNJ-3989 (or PegIFN- $\alpha$ 2a) that persists despite changing tenofovir disoproxil to ETV or TAF (if the patient was receiving tenofovir disoproxil) (see Section 8.5.6.4).
- The participant has a confirmed QTcF prolongation (defined as a QTcF value of  $>500$  ms, or an increase from baseline of  $>60$  ms) at any given time point.
- The participant requires  $\geq 7$  days of treatment with any of the disallowed medications listed in Section 6.5 and does not intend to discontinue treatment with the disallowed medication.

- The participant has confirmed HBV virologic breakthrough (ie, confirmed on-treatment HBV DNA increase by  $>1 \log_{10}$  IU/mL from nadir or confirmed on-treatment HBV DNA level  $>200$  IU/mL in participants who had HBV DNA level  $<\text{LLOQ}$  of the HBV DNA assay). In case of virologic breakthrough, the same assessments will be done at an unscheduled visit as will be done in case of an ALT flare, but no PBMC sample will be taken (see Section 8.5.6.1 and Schedule of Activities), changing the NA should be considered in consultation with the sponsor.

If virologic breakthrough occurs during JNJ-3989 and PegIFN- $\alpha$ 2a administration, this does not automatically lead to stop of JNJ-3989 and/or PegIFN- $\alpha$ 2a but should be assessed/discussed with the Sponsor.

In case of virologic breakthrough, a viral sequencing sample will be collected at the next visit.

- The participant has ALT/AST elevations, as described in Section 8.5.6.2.
- The participant has confirmed  $\geq$ grade 3 hematologic abnormalities as described in Section 8.5.6.5.

**NOTE:** The grades are based on the DAIDS Toxicity Grading Scale (see Section 10.9, Appendix 9, DAIDS Table).

In addition, PegIFN- $\alpha$ 2a (if applicable) must immediately be discontinued for any of the following reasons:

- Participant has platelet count  $<25,000$  cells/mm $^3$
- Participant has ANC  $<500$  cells/mm $^3$

**Note:** PegIFN- $\alpha$ 2a treatment can be restarted when ANC values return to more than 1,000 cells/mm $^3$  (see details in Section 6.6, Dose Modification)

- Participant develops evidence of hepatic decompensation during treatment, or ALT increase clinically significant or accompanied by direct bilirubin increase
- Participant develops thyroid disorders or diabetes during treatment and cannot be controlled with medication
- Participant develops new or worsening ophthalmologic disorders
- Participant develops any deterioration of cardiovascular status
- Participant develops serious, acute hypersensitivity reaction (eg, urticaria, angioedema, bronchoconstriction, anaphylaxis)
- Participant develops serious infection (bacterial, viral, fungal) and/or sepsis
- Participant develops persistent or unexplained pulmonary infiltrates or pulmonary function impairment
- Participant with onset or worsening of psoriatic lesion
- Participant develops moderate or severe depression, or other psychiatric symptoms (for mild depression, treatment discontinuation may be considered)

**Note:** Participants who develop a neuropsychiatric AE during optional PegIFN- $\alpha$ 2a treatment, will be monitored closely until the neuropsychiatric AE resolves, with frequent (at least weekly) follow-up phone calls.

- Participant develops colitis symptoms (such as but not limited to abdominal pain, bloody diarrhea, and fever)
- Participant develops symptoms or signs suggestive of pancreatitis

If a participant discontinues investigational intervention for any reason before Week 48, then the early withdrawal assessments should be obtained. The participant will enter the follow-up phase and complete the follow-up schedule unless the participant withdraws consent. Participants who withdraw consent will be offered an optional safety follow-up visit to occur on the day of consent withdrawal. Study intervention assigned to the participant who discontinued study intervention may not be assigned to another participant.

In case a participant withdraws consent for the second biopsy, the study participant may continue the study intervention and visit schedule as outlined in the [Schedule of Activities](#).

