**Table 5: PegIFN- $\alpha$ 2a Hematological Dose Modification Guidelines**

Laboratory Values	Recommended Dose
ANC <750 cells/mm 	Reduce to 135 $\mu$ g
ANC <500 cells/mm 	Discontinue treatment until ANC values return to more than 1,000 cells/mm  . Reinstitute at 90 $\mu$ g and monitor ANC.
Platelet <50,000 cells/mm 	Reduce to 90 $\mu$ g
Platelet <25,000 cells/mm 	Discontinue treatment

ANC: absolute neutrophil count

Source: Pegasys USPI and SmPC

For participants who prematurely discontinue PegIFN- $\alpha$ 2a, treatment with PegIFN- $\alpha$ 2a may be restarted according to the recommendations from the locally approved prescribing information for PegIFN- $\alpha$ 2a.

### 6.6.1. Study Intervention Completion at Week 48

With the implementation of Protocol Amendment 5, all participants had to stop JNJ-6379 treatment immediately.

Participants will complete treatment with JNJ-3989 after a fixed duration of 48 weeks. If all of the below criteria are met based on clinical laboratory tests performed at Week 44, treatment with NA will also be completed at the next scheduled visit (ie, Week 48):

- The participant has ALT <3x ULN, AND
- The participant has HBV DNA <LLOQ, AND
- The participant is HBeAg negative, AND
- The participant has HBsAg <10 IU/mL.

**Note:** In case of ALT elevation  $\geq 3$ x ULN at Week 44 the investigator must consider different potential causes of increased ALT to ensure appropriate work up and management as needed. If the ALT elevation is unrelated to HBV activity and/or <3x ULN by Week 48, NA completion may be considered at the discretion of the investigator and in consultation with the sponsor.

Participants who do not meet the above criteria at Week 48 should continue NA treatment during the 48-week follow-up phase. Participants who are receiving optional treatment with PegIFN- $\alpha$ 2a and who have not met NA treatment completion criteria at Week 48 may have NA treatment completion criteria assessed at the end of treatment with PegIFN- $\alpha$ 2a and stop NA if criteria are met.

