If a participant prematurely discontinues investigational intervention before Week 48, follow-up assessments should be obtained as per the [Schedule of Activities](#) until 48 weeks after the end of investigational intervention unless the participant withdraws consent. In this case, NA treatment may be continued or, in consultation with the sponsor, discontinued, based on the above-mentioned NA treatment completion criteria.

With the implementation of Protocol Amendment 5, the follow-up period will be extended for participants who are receiving optional treatment with PegIFN- $\alpha$ 2a and who meet NA treatment completion criteria at the end of treatment with NA and PegIFN- $\alpha$ 2a to ensure all participants have at least one year of follow-up after NA treatment cessation.

The investigator should consider to re-start NA treatment per local standard of care at the EOS visit (Follow-up Week 48 up to maximum Follow-up Week 72) for participants who met the NA treatment completion criteria at Week 48 or for participants who met NA treatment completion criteria at the end of treatment with PegIFN- $\alpha$ 2a during the follow-up phase, who did not re-start NA treatment during the follow-up phase, and who did not achieve and maintain HBsAg seroclearance. NA will not be provided by the sponsor after the final study visit.

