the participant should discontinue JNJ-3989 (and PegIFN- $\alpha$ 2a, if applicable) and should be monitored on a weekly basis or as per good clinical practice until ALT and AST levels have returned to  $<5$  x ULN and HBV DNA is  $<20,000$  IU/mL and, if present, liver-related symptoms have improved. NA treatment should be continued. Additional tests should be considered based on clinical judgement (refer to Section 10.6, Appendix 6, Intervention-emergent ALT/AST Elevations).

In case of prolonged ALT elevation  $>3$  x ULN AND  $>2$  x nadir, which lasts at least 12 weeks, the decision to continue JNJ-3989 and/or PegIFN- $\alpha$ 2a should be based upon virologic parameters (eg, HBsAg, HBV DNA) and should be made in consultation with the sponsor.

PegIFN- $\alpha$ 2a may need to be discontinued in clinically significant cases of ALT increase or in combined increase of ALT and direct bilirubin. Refer to the prescribing information for PegIFN- $\alpha$ 2a.

The NA re-treatment criteria during follow-up are presented in Section 6.6.2.

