### **Continuation of study intervention:**

- Any issue with continuation and/or provision of study intervention should be discussed with the sponsor and should be well documented.
- Study intervention should be continued if, in the assessment of the investigator, it does not result in risk to the participant. If at any time the participant's safety is considered at risk due to study intervention, study intervention will be temporarily or permanently discontinued, while every effort should be made to maintain follow-up on study. The benefit of continuing study intervention should be assessed by the investigator for each individual participant, considering the potential impact of reduced direct clinical supervision on participant safety.
- If a participant develops a SARS-CoV-2 infection, the investigator should contact the sponsor to discuss plans for study intervention and follow-up. A decision to continue study intervention should be made by the investigator depending on symptoms and concomitant medication(s) used for the treatment of COVID-19. Study intervention must be discontinued if prohibited medication is used.

- When a participant, for whom study intervention has been interrupted, recovers from suspected or confirmed SARS-CoV-2 infection or related disease and all AEs related to SARS-CoV-2 infection improve to Grade ≤1, the investigator should discuss with the sponsor about resuming study intervention.

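### After an early stop of JNJ-3989, Protocol 7.1 and 6.6.1 give different bases for stopping NA, and the SARS-CoV-2 rule in Appendix 11, as worded, stops NA as well

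*Protocol*

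**What the plan says.** Protocol 7.1 lists the events on which JNJ-3989 and/or PegIFN-α2a must be stopped. On NA it says: "NA treatment may be continued or, in consultation with the sponsor or discontinued based on investigator judgement". Its reach is general: "If a participant discontinues investigational intervention for any reason before Week 48, then the early withdrawal assessments should be obtained". One listed event reads "The participant has signs of hepatic decompensation (ie, clinical evidence of ascites, bleeding varices, or hepatic encephalopathy"); a laboratory alternative follows, namely direct bilirubin above 1.5x ULN combined with INR of at least 1.5x ULN or albumin below 3.0 g/dL.

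Protocol 6.6.1 also covers a stop of investigational intervention before Week 48. It says: "NA treatment may be continued or, in consultation with the sponsor, discontinued, based on the above-mentioned NA treatment completion criteria". Those are the criteria for the regular end of treatment, introduced by "If all of the below criteria are met based on clinical laboratory tests performed at Week 44": ALT below 3x ULN, HBV DNA below LLOQ, HBeAg negative, and HBsAg below 10 IU/mL.

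Protocol 6.6.2 says when NA should be restarted after a stop. Its first trigger is "Immediately with signs of decreasing liver function based on laboratory findings (eg, INR, direct bilirubin) or clinical assessment (eg, ascites, hepatic encephalopathy"). Protocol 8.5.6.2 stops JNJ-3989 when raised ALT/AST comes with signs of reduced liver function, and adds: "NA treatment should be continued. Additional tests should be considered based on clinical judgement".

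Protocol Appendix 11, in the bullet on SARS-CoV-2 infection, says: "Study intervention must be discontinued if prohibited medication is used". The Synopsis, Section 2 and the definitions in Appendix 1 all include NA in study intervention.

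**The concern.** Protocol 2.3.2.2 states that stopping NA carries a risk of hepatitis B flares. Section 6.6.1 controls that risk with four laboratory criteria and sponsor consultation. A site that works from 7.1 can stop NA in a participant who fails all four criteria and still be within the protocol. Two sites facing the same event could therefore act differently, and neither would record a deviation.

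The sharpest case is hepatic decompensation, where 7.1 allows NA to be withdrawn although 6.6.2 treats the same signs as a reason to restart it immediately.

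The Appendix 11 sentence is mandatory rather than permissive. Read with the protocol's own definition, it withdraws NA for any use of a prohibited medicine during SARS-CoV-2 infection, however short. What is at stake is participant safety and uniform conduct, more than the estimates.

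**Working it through.** No figure in the plan is in question, so the check sets the texts side by side.

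**1. Same event, two bases.** The intervention table in Protocol 6.1 classes JNJ-3989 as investigational and the NAs as background. A JNJ-3989 stop before Week 48 therefore falls under both sections.

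| | 7.1 | 6.6.1 |
|---|---|---|
| NA may continue | yes | yes |
| NA may stop | yes | yes |
| Basis for stopping | investigator's judgement | four completion criteria |
| Sponsor consulted | unclear (garbled) | yes |
| Refers to the other section | no | no |

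A site that follows 6.6.1 also satisfies 7.1. A site that follows 7.1 need not satisfy 6.6.1.

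**2. What event-specific text settles.**

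| Reason for stopping JNJ-3989 | NA instruction | Where |
|---|---|---|
| ALT/AST elevation | continue | 8.5.6.2 |
| Hematologic abnormality | continue | 8.5.6.5 |
| Rash needing systemic steroid above 5 mg/day | may continue | 8.5.7.1 |
| Allergic reaction; grade 3 or 4 rash | may stop on judgement after consulting the sponsor | 8.5.7.2; Table 6 |
| Pregnancy | none | 8.5.5 |
| Renal abnormality that persists | switch from tenofovir disoproxil first; nothing once JNJ-3989 is finally stopped | 8.5.6.4 |
| QTcF prolongation | none | 7.1 |
| Decompensation without raised ALT/AST | none | 7.1 |

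The last four rows fall back on the two general rules.

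**3. Decompensation.**
- The instruction in 8.5.6.2 to keep NA applies only when ALT and/or AST is at least 3x ULN and at least 3x nadir.
- The first restart trigger in 6.6.2 gives four examples: INR, direct bilirubin, ascites and encephalopathy. All 4 of 4 appear in the 7.1 decompensation criterion.
- Section 6.6.2 acts only after NA has been stopped. It is a backstop and does not prevent the stop.
- The completion criteria use ALT, HBV DNA, HBeAg and HBsAg. Of these 4, 0 are bilirubin, INR or albumin, so a bare cross-reference to 6.6.1 would not close this gap.

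**4. Appendix 11 against 7.1.**

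| | Appendix 11, SARS-CoV-2 bullet | 7.1, disallowed medication |
|---|---|---|
| What stops | study intervention (NA included by definition) | JNJ-3989 and/or PegIFN-α2a |
| Minimum duration | none | 7 days |
| Intent to continue the medicine | not considered | required |

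A course of 1 to 6 days meets the Appendix 11 wording but not the 7.1 criterion.

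**5. Analysis.** SAP 5.2 already lists NA discontinuation and re-treatment for early discontinuers. SAP 5.4.2.4.6 summarises who met the completion criteria. SAP 5.4.2.5 counts participants who discontinue treatment before Week 48 (other than JNJ-6379) as non-responders for functional cure, so a judgement-based stop cannot create a cure.

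**The case against.** The best reply is that 7.1 contains a slip, not a policy. The allergic-reaction text and Table 6 use nearly the same words with the sponsor clause in the right place, and 8.2 makes the investigator responsible for checking the 6.6.1 criteria. This explains the grammar. It does not remove the difference, because the repaired sentence would still rest on judgement where 6.6.1 rests on criteria.

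The decompensation gap is also narrow. Cirrhosis, portal hypertension and past decompensation are excluded at entry, the gap needs ALT and AST both below the 8.5.6.2 threshold, and an investigator would have to choose to stop NA. That stands, and it limits how often the gap could matter.

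On Appendix 11, the protocol uses study intervention loosely: Sections 1.3.1 (footnote d) and 1.3.2 speak of it as ended while NA continues. The appendix allows for temporary stops and for resumption, asks for sponsor contact and a benefit-risk analysis, and preserves investigator judgement. All of this stands. It makes harm less likely but leaves the sentence in conflict with 7.1.

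Three stronger inferences are not supported:
- **That 7.1 and 6.6.1 contradict each other.** Both say may, and a site can comply with both.
- **That the severe flare described in 4.2 shows the danger of judgement-based stops.** That NA stop, in another study's control arm, followed protocol-defined criteria. The response was closer monitoring and revised re-treatment rules. The purpose that 4.2 gives for the completion criteria likewise concerns participants who completed 48 weeks.
- **That about 5 participants are exposed (0.20 × 24 = 4.8).** The 20% in 9.2 is a dropout allowance. SAP Attachment 1 uses it for loss of usable data, and 7.2 keeps a participant who stops study intervention in the study.

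**Conclusion.** The point holds as a wording conflict with a safety consequence. For a JNJ-3989 stop before Week 48, the protocol gives two bases for stopping NA and no order of precedence. Event-specific text leaves at least four situations to those general rules. In one of them, decompensation without raised ALT/AST, 7.1 permits what 6.6.2 would immediately undo. Appendix 11, as worded, extends a mandatory stop to NA and drops the 7-day and intent conditions of 7.1.

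The conclusion on Appendix 11 rests on the protocol's definition of study intervention. A reader might infer that the sponsor intends to withdraw NA for a short course of COVID-19 medication. The documents do not show this; JNJ-3989 and PegIFN-α2a are probably what was meant.

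The number of participants affected is unknown, because the plan gives no rate of early JNJ-3989 stops, and it may be 0. The effect on the analysis is small.

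**What to change.** 1. In Protocol 7.1, replace the NA sentence with:

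> If JNJ-3989 is discontinued before Week 48 in a participant receiving NA, NA should be continued unless, in consultation with the sponsor, the completion criteria in Section 6.6.1 are met or there is an NA-specific safety reason or contraindication. NA should not be stopped on the completion criteria alone in a participant with signs of hepatic decompensation. Event-specific NA instructions in Sections 8.5.6, 8.5.7 and Table 6 take precedence. Discontinuing PegIFN-α2a alone does not change NA treatment.

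The opening condition and last sentence are needed because 7.1 also governs PegIFN-α2a-only stops, which can occur after Week 48 in participants already off NA.

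2. In Protocol 6.6.1, add a cross-reference to this rule from the early-stop sentence.

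3. In Appendix 11, replace the prohibited-medication sentence with:

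> JNJ-3989 (and PegIFN-α2a, if applicable) must be discontinued if the disallowed-medication criterion in Section 7.1 is met. NA should be continued, or switched in consultation with the sponsor if the medication is prohibited by the NA prescribing information.

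The cost is protocol wording in three places, with no new data, visits or participants and no SAP change. The downside is that investigators lose some latitude in 7.1, and an NA stop outside the listed exceptions would be recorded as a deviation.
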